### 7.1.1. Discontinuation of JNJ-3989

Treatment with JNJ-3989 must be discontinued if any of the following occurs:

- The participant withdraws consent to receive study intervention.
- The investigator believes that for safety reasons or tolerability reasons (eg, AE) it is in the best interest of the participant to discontinue JNJ-3989.
- The participant becomes pregnant.
- The participant has  $\geq$ Grade 3 rash (see Section 10.6, Appendix 6: Rash Management).
- The participant has  $\geq$ Grade 3 allergic reaction or worsening of Grade 2 allergic reaction (see Section 8.3.6.4.1, Acute Systemic Allergic Reactions).
- The participant has signs of hepatic decompensation (ie, clinical evidence of ascites, bleeding varices, or hepatic encephalopathy) or an increase in direct bilirubin  $>1.5x$  ULN in combination with INR  $\geq 1.5x$  ULN or albumin  $<3.0$  g/dL. Alternative treatment options (outside the study) should be considered in consultation with the sponsor.
- The participant has treatment-emergent ALT/AST elevations, as described in Section 8.3.6.1, Intervention-emergent ALT/AST Elevations including immune-related hepatic AEs.
- The participant has a confirmed  $\geq$ Grade 3 eGFR abnormality and a drop from baseline of  $>10$  mL/min/1.73 m^2, based on creatinine (calculated by the CKD-EPI formula), that persists despite changing tenofovir disoproxil to ETV or TAF (if the participant was receiving tenofovir disoproxil) and that is considered at least possibly related to JNJ-3989.
- The participant has a QTcF prolongation (defined as a QTcF value of  $>500$  ms, or an increase from baseline of  $>60$  ms) at any given time point.
- The participant requires  $\geq 7$  days of treatment with any of the disallowed medications listed in Section 6.5, Concomitant Therapy, and does not intend to discontinue treatment with the disallowed medication.
- The participant has confirmed HBV virologic breakthrough (ie, confirmed on-treatment HBV DNA increase by  $>1$  log10 IU/mL from nadir or confirmed on-treatment HBV DNA level  $>200$  IU/mL in participants who had HBV DNA level  $<$ LLOQ of the HBV DNA assay). If virologic breakthrough occurs during nivolumab administration, this does not automatically lead to stop of JNJ-3989 and/or nivolumab, but should be assessed/discussed with the sponsor.

In case of virologic breakthrough, a viral sequencing sample may be collected at the next visit.

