## **D)** Intercurrent events:

- Treatment discontinuation prior to Week 24: if the participant discontinued treatment prior to Week 24 then s/he will be considered non-responder (composite strategy).
- Major protocol deviations affecting efficacy: Table 9 identifies the deviations considered intercurrent event. Participants with such deviations and who have missing data for the endpoint will be considered as non-responders (composite strategy). For all other deviations not considered intercurrent events, the data are used regardless of the occurrence of major protocol deviations (treatment policy strategy).

- Deaths prior to FU Week 24 are handled in a composite strategy as participants who die prior to FU Week 24 will be considered as non-responders.
- **E)** Population-level summary:
  - **a. Primary (comparison vs fixed external proportion):** Difference in proportion of participants with HBsAg seroclearance at FU Week 24 using a fixed external proportion of 1%.
  - **b.** Secondary (comparison amongst regimens): Difference in proportion of participants with HBsAg seroclearance at FU Week 24 between study intervention arms.

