# 5.3.2.1.4. Missing Data Handling Rule

Participants who withdraw from the study prior to FU Week 24 will be considered as non-responders.

If a participant remains in the study after experiencing a major protocol deviation (defined for the purpose of efficacy analyses and is an intercurrent event) and has missing FU Week 24 value, then the imputation to non-response will be applied. If the value for the endpoint at FU Week 24 is available, then such data will be used to determine their response status.

For the participants still in the study at FU Week 24 or for participants that have neither discontinued treatment early nor experienced any major protocol violations (defined for the purpose of efficacy analyses and is an intercurrent event), and HBsAg values missing at FU Week 24, then the primary method to handle missing data will be the missing as non-responder (MANR).

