#### 5.3.3.1.2. Data Included

FU Week 24 response status data from randomized participants that are included in the PP analysis set will be used, after taking into account the intercurrent events and applying the intercurrent event strategies specified in Section 5.3.3.

To complement this analysis because of its inherent bias and allow a better interpretation of the results, the proportions of participants excluded from the PP analysis set will be summarized by intervention arm and by type of major protocol deviation.

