31	Participants having used any invasive investigational medical device within 6 months or having received an investigational intervention or a biological product, immunoglobulin or other blood product not intended for the treatment of HBV within 6 months or 5 half-lives (whichever is longer), before the planned first dose of study intervention, or is currently enrolled in an interventional clinical study with an investigational product.	Exclusion criterion A17 (adapted from M17) met: Participant used any invasive investigational medical device within 6 months or having received an investigational intervention or a biological product, immunoglobulin or other blood product not intended for the treatment of HBV within 6 months or 5 half-lives (whichever is longer), before the planned first dose of study intervention, or is currently enrolled in an interventional clinical study with an investigational product.	Entered but did not satisfy criteria	Yes	No
42	Participants who received or plans to receive any live vaccine within 28 days before the planned first dose of study intervention until the end of the study. Note: Non-live vaccines approved or authorized for emergency use by local health authorities are allowed. For this study, the second dose of Sputnik V COVID-19 vaccine is considered a live vaccine.	Exclusion criterion A28 met: Participant received or plans to receive any live vaccine within 28 days before the planned first dose of study intervention until the end of the study.	Entered but did not satisfy criteria	Yes	No

Table 9: Selected Major Protocol Deviations for Analysis Purposes

Sequence	Description	Protocol Deviation	Protocol	Exclude	Intercurrent Event
(as reported in MPD)		as entered in Study Specific Issue System	Coded Term (DVDECOD)	ITOM FF	Event
44	
 
Disallowed from 12 months prior to screening until end of follow-up: 
 
IFN.
 
Any oligonucleotide-based treatment (eg, siRNA, nucleic acid polymers, antisense oligonucleotides), other than the study intervention taken in the context of this study.
 
Any prior treatment with an anti-PD-1 antibody, anti-PD-L1 antibody or anti-PD-L2 antibody, other than the study intervention taken in the context of this study.
 

	Received disallowed medication from 12 months prior to screening until end of follow-up < specify treatment, dose, unit, frequency, reason administered >.	Received a disallowed concomitant treatment	Yes	Yes

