45	
 
Disallowed from 6 months prior to screening until end of follow-up:
 
Any investigational agent, investigational vaccine, invasive investigational medical device, or investigational biological product (other than the study intervention taken in the context of this study).
 
Note: For investigational COVID-19 vaccines administered within 6 months prior to screening, an exception will be made as long as the vaccine has been approved (or received emergency use authorization or conditional marketing authorization) at the time of screening.
 
	Received disallowed medication from 6 months prior to screening until end of follow-up < specify treatment, dose, unit, frequency, reason administered >.	Received a disallowed concomitant treatment	Yes	Yes
	
 
Any systemically (eg, intravenously, intramuscularly, orally, subcutaneously) administered medication
 
				

 Table 9:
 Selected Major Protocol Deviations for Analysis Purposes

Sequence number (as reported in MPD)	Description	Protocol Deviation Description (DVTERM) as entered in Study Specific Issue System	Protocol Deviation Coded Term (DVDECOD)	Exclude from PP	Intercurrent Event
	that directly or indirectly interferes with immune responses (eg, cyclosporine, interleukins, systemic corticosteroids at doses exceeding 5 mg/day of prednisone or its equivalent). Use of systemic immunosuppressive medications for the management of irAEs, ISRs, or IRRs, or in participants with contrast allergies is acceptable, ie, it will not be considered a protocol deviation, but it will lead to nivolumab discontinuation and/or JNJ-3989 discontinuation if criteria relative to the use of prohibited medication (including systemic corticosteroids) detailed in Clinical Protocol Sections 7.1.1 and 7.1.2 are met. In addition, use of inhaled, topical, local, and intranasal corticosteroids is permitted.				
46	
 
Disallowed from screening until end of follow-up:
 
Any anti-HBV drug (including vaccines) other than the study intervention and the NA background regimen taken in the context of this study.
 
Notes: Prior hepatic treatment with herbal or nutritional products is allowed but should be stopped at screening.
 
Biotin (>1 mg daily dose), either taken alone or as
 
	Received disallowed medication from screening until end of follow-up < specify treatment, dose, unit, frequency, reason administered >.	Received a disallowed concomitant treatment	Yes	Yes

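### The SAP labels its handling of Table 9 intercurrent events composite, but the rule fails only missing HBsAg, so clearance after a prohibited anti-HBV agent counts as response in the main estimator

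*SAP*

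**What the plan says.** The primary endpoint is HBsAg below LLOQ at FU Week 24, tested in each arm against a fixed 1% (SAP 5.3.1 and 5.3.2.1.1.1). SAP 5.3.2 D lists three kinds of intercurrent event. Treatment discontinuation before Week 24 and death before FU Week 24 are failures with no further condition. For deviations flagged in Table 9 the text adds a condition: "Participants with such deviations and who have missing data for the endpoint will be considered as non-responders (composite strategy". All other deviations are assigned to treatment policy.

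SAP 5.3.2.1.4 repeats the condition. After a flagged deviation with a missing FU Week 24 value, non-response is imputed; otherwise "If the value for the endpoint at FU Week 24 is available, then such data will be used to determine their response status". Participants who withdraw before FU Week 24 are non-responders. For participants still in the study, or with no early discontinuation and no flagged deviation, whose HBsAg is missing, "then the primary method to handle missing data will be the missing as non-responder (MANR".

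Table 9 (SAP 6.4) marks these medication rows both as intercurrent events and as per-protocol exclusions:

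- Row 44, "Received disallowed medication from 12 months prior to screening until end of follow-up": interferon, other oligonucleotide treatments, other PD-1, PD-L1 or PD-L2 antibodies.
- Row 45, "Received disallowed medication from 6 months prior to screening until end of follow-up": investigational agents and systemic immune-active drugs. Treatment of irAEs, ISRs or IRRs is expressly not a deviation.
- Row 46, "Received disallowed medication from screening until end of follow-up": other anti-HBV drugs, together with biotin and occluded topical steroids.

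Dosing rows 47, 48 and 52 to 54 are also flagged as intercurrent events.

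**The concern.** Under a composite strategy the event itself is part of the outcome: once it occurs, the participant has failed, whatever the later HBsAg value. The rule attached to the label does not do that. It lets HBsAg clearance after another agent that acts on HBV count as success of the JNJ-3989, nivolumab and NA regimen, in a test meant to show that this regimen exceeds 1%.

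The consequence could be large because the rejection threshold is a very small count. A reader who trusts the label would also believe that such cases had been failed when they had not.

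**Working it through.** **Step 1: what the flag does in the main estimator (SAP 5.3.2 D and 5.3.2.1.4).**

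| FU Week 24 HBsAg | Flagged deviation | No flagged deviation |
|---|---|---|
| Observed | Observed value decides | Observed value decides |
| Missing | Non-responder | Non-responder (withdrawal rule or MANR) |

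The columns are identical, so the flag has no effect here. It acts only in sensitivity estimators 2 and 3 (SAP 5.3.2.2.2.2 and 5.3.2.2.3.2). There it decides whether a participant with a missing value is failed, rather than dropped or filled from a nearby visit. In both, clearance observed after the event still counts as response.

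**Step 2: what else could catch a case.** Protocol 7.1.1 requires JNJ-3989 to be discontinued when a participant needs at least 7 days of a disallowed drug "and does not intend to discontinue treatment with the disallowed medication". If that happens before Week 24, the participant fails. Not caught are shorter use before Week 24, failure to apply that rule (Table 9 row 64, which is not flagged as an intercurrent event), and any agent started between Week 24 and FU Week 24. That last window is 24 of the 48 weeks from Day 1 to the endpoint. The supplementary per-protocol estimand excludes rows 44 to 46 and row 64, but it does not alter the main estimand.

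**Step 3: reproduce the plan's power.** The inputs, from SAP section 3, are a null of 1% and differences of 15 and 20 points, that is, rates of 16% and 21%. The critical count is two responders at both 0.05 and 0.025. With 20 per arm the power is 85.3% and 94.3% (stated: at least 85%). With 16 per arm it is 75.1% and 87.9% (stated: at least 75%). The stated figures reproduce.

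**Step 4: the threshold at the final sizes, 18 and 19.** The exact one-sided p-value is P(X ≥ r), with X binomial (n, 0.01).

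| Responders r | n=18 | n=19 |
|---|---|---|
| 1 | 0.165 | 0.174 |
| 2 | 0.0138 | 0.0153 |
| 3 | 0.0007 | 0.0009 |

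Under Hochberg, an arm with two responders has p below 0.025 and is rejected whatever the other arm shows. An arm with one has p above 0.05 and is never rejected. Reclassifying one participant therefore changes the decision in an arm with exactly two responders. By itself it does not change an arm with three or more.

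**Step 5: how often an arm sits on that edge.** At the planned rates, P(X=2) is 0.241 in Arm 1 (n=18, 16%) and 0.137 in Arm 2 (n=19, 21%). The primary hypothesis needs only one arm, so it rests on an arm with exactly two responders only if the other arm has at most one. The chances of at most one are 1 − 0.808 = 0.192 (Arm 1) and 1 − 0.931 = 0.069 (Arm 2). Hence 0.241 × 0.069 + 0.137 × 0.192 = 0.043, or about 4%. At assumed true rates of 5% to 10% in both arms, the same calculation gives 25% to 27%. None of these figures includes the chance that one of the two responders took a prohibited agent, which the documents do not give.

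**Step 6: what the per-protocol analysis would show.** Suppose an arm has one unaffected responder and one who cleared after a prohibited agent. As written, the arm has 2/18 (p=0.0138) or 2/19 (p=0.0153). Removing the second participant gives 1/17 (p=0.157) or 1/18 (p=0.165). A true composite gives 1/18 (p=0.165) or 1/19 (p=0.174). Neither alternative rejects.

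**The case against.** The strongest reply is that this is a wrong label, not a broken rule. SAP 5.3.2 D and 5.3.2.1.4 give the same explicit instruction, it can be programmed, and treatment policy is a legitimate strategy. Nothing shows that the label, rather than the twice-stated rule, expresses the intent. This stands, and it is why the first remedy is to correct the label.

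Second, a deciding case would already be visible. The per-protocol analysis would lose the rejection (step 6), and "the proportions of participants excluded from the PP analysis set will be summarized by intervention arm and by type of major protocol deviation". This also stands, with two limits: that analysis is supplementary, and it removes participants for other deviations too.

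Third, SAP Amendment 2 followed the primary results and the trial is open-label. Any new rule that asks someone to judge whether an agent might affect HBV would add discretion after outcomes are known. This stands and restricts the added analysis to agents that Table 9 already names.

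A reader might also infer that the rule inflates the Type 1 error. With both arms truly at 1%, the chance of any rejection is 1 − (1 − 0.01376)(1 − 0.01527) = 2.9%. Counting one post-agent clearance raises it to 1 − 0.99^17 × (1 − 0.01527) = 17.0% (case in Arm 1) or 1 − (1 − 0.01376) × 0.99^18 = 17.7% (Arm 2). These figures assume that such a case has occurred. They are conditional probabilities and cannot be set against the 5% level. If q is the chance of one such case, the overall rate is about 2.9% plus q times 14 to 15 points, which passes 5% only if q exceeds about 14% to 15%. The documents support no such value.

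**Conclusion.** The label in SAP 5.3.2 D is wrong for the rule it describes. In the main estimator, Table 9 intercurrent events are handled by treatment policy, with missing values as non-response. HBsAg clearance after a row 44 agent or another anti-HBV drug in row 46 is counted as response unless treatment was discontinued before Week 24. Protocol 7.1.1 and the per-protocol estimand narrow this gap without changing the main estimand.

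The size is conditional. One such participant would decide an arm with exactly two responders, moving p from 0.014–0.015 to 0.165–0.174. At the planned rates, the chance that the primary claim rests on such an arm is about 4%, before allowing for whether a prohibited agent was taken. The calculation assumes all 18 and 19 randomized participants are in the FAS.

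The documents do not support the inference that such a case occurred or that the primary result is unsound. Nor does this point turn on which agent is meant by treatment discontinuation. SAP 1.2 and Protocol section 7 separate stopping nivolumab alone from stopping JNJ-3989 or all study intervention, and the SAP version history records that the protocol amendment for the nivolumab halt was agreed not to affect the SAP. Naming the agent would be a useful clarification, no more.

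**What to change.** Amend SAP 5.3.2 D and 5.3.2.1.4 together.

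1. Relabel the rule as written: treatment policy, with missing values as non-response. Apply this label to all flagged Table 9 rows, including dosing rows 47, 48 and 52 to 54.
2. Add one run of the 1% test with Hochberg under a true composite. Any participant with a row 44 deviation, or a row 46 deviation for an anti-HBV drug, starting between Day 1 and FU Week 24 is a non-responder even when HBsAg is observed. Use the agents as Table 9 names them, with no judgement of likely effect. Leave out biotin, topical steroids and treatment of irAEs, ISRs or IRRs.
3. Mark this run as post hoc to the primary analysis, and report it beside the result under the SAP's current classification and the per-protocol result.

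The cost is a few sentences, one check of start dates for row 44 and row 46 deviations, and one extra run. If no participant took such an agent, no result changes and the report can say so.

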# 5.3.2.1. Main Estimator

# 5.3.2.1.1. Analysis Methods

# 5.3.2.1.1.1. Comparison vs Fixed External Control

The main estimator is constructed by using an exact binomial test against a fixed external control value of 1% at a one-sided Type 1 error rate of 0.05 and applying the Hochberg procedure for adjusting for multiple comparisons (Section 5.3.4).

# 5.3.2.1.1.2. Comparison Amongst Regimens

The main estimator is constructed by using the Mantel-Haenszel test (Mantel N. et al., 1959) adjusted for the randomization stratification factor (HBsAg level at screening [<100 IU/mL, 100 to <1,000 IU/mL, and  $\geq$ 1,000 IU/mL]) to compare the primary endpoint between the intervention arms at a one-sided alpha level of 0.05.

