#### **VERSION HISTORY**

Document History	
Document	Date
Original SAP	20 September 2022
Amendment 1	23 August 2023
Amendment 2	10 June 2024

Amendment 2 (10 June 2024)

The main purpose of this SAP amendment is to document changes in the scope of the final analyses, based on results of the primary analysis.

Section number and Name	Description of Change	Brief Rationale
5.3.6. Comparisons Between Arm 1, 2 and Model-Based Virtual Nivolumab-Free JNJ- 3989+NA Regimen Control	Section Removed.	Virtual Control analysis is no longer of interest.
5.4.1.2. Continuous Endpoints	Section Updated.	Change from baseline value to the nadir is of interest only in HBsAg.
5.4.2.1.1. HBsAg Cut-offs and 5.4.2.1.4. HBeAg Cut- offs	Section Removed.	Cross-Tabulation for Quantitative Result vs. Qualitative Result Over Time for HBsAg and HBeAg removed as according to the protocol, qualitative HBsAg and HBeAg are only collected at screening and baseline.
5.4.2.2.1. HBsAg, HBeAg, HBV DNA and ALT	Section Updated.	
 
Waterfall plots of changes from Reference Timepoints in HBsAg removed
 
Descriptive statistics of changes from RTs in ALT removed
 
Changes from baseline analyses are removed for HBV DNA
 
Changes from baseline outputs are only displayed in the log 10 scale for all viral parameters
 
Change from Nivolumab RT and Follow-up Week 4 RT are of interest only for HBsAg
 

Section number and Name	Description of Change	Brief Rationale
5.5.1.3. and 5.5.2.3. Endpoints for Correlation	Section Removed.	Endpoints for Correlation is no longer of interest.
5.5.2.2.2. HBV RNA and HBcrAg	Section Removed.	Change from baseline value to the nadir is of interest only in HBsAg.
5.3.5. Subgroup Analyses of Primary Efficacy Endpoint and 5.7.6. Definition of Subgroups	Section Removed.	Subgroup Analysis is removed due to low number of observed events of interest.

## Amendment 1

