# 2. STATISTICAL HYPOTHESES

The primary hypothesis of this study is that at least one of the combination regimens of JNJ-3989+nivolumab+NA is more efficacious than JNJ-3989+NA treatment, as measured by the primary efficacy endpoint (ie, the proportion of participants with HBsAg seroclearance at FU Week 24). Because the study does not include a regimen arm without nivolumab, the hypothesis is formulated assuming a fixed response rate for JNJ-3989+NA of 1% based on previous study 73763989HPB2001 (REEF-1).

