# 3. SAMPLE SIZE DETERMINATION

According to the initial protocol, a sample size of 20 participants per intervention arm which yielded  $\geq$ 85% statistical power to detect a  $\geq$ 15% and  $\geq$ 20% difference for the proportions of participants with HBsAg seroclearance at FU Week 24 in the 2 intervention arms, respectively, vs a fixed proportion of 1%. Statistical power to test the primary hypothesis was assessed for each of the intervention arms, using an exact test for a single proportion with a one-sided Type 1 error rate of 0.05 and applying the Hochberg procedure for multiple comparisons adjustment. The fixed rate assumed for the external active control (JNJ-3989 [200 mg]+NA treatment) is based on the data of study 73763989HPB2001 (REEF-1).

The total study sample size was adjusted to 44 participants (22 per arm) with 1:1 randomization ratio to each of the intervention arms, to account for an approximate 10% attrition rate.

Due to the decision to not extend further enrollment beyond the planned enrollment period and proceed with a reduced sample size, the final sample size is 37 (18 in Arm 1 and 19 in Arm 2). Under the same assumptions and methods of the initial protocol, an approximate sample size of 16 participants per intervention arm (assuming 10% attrition) yields  $\geq$ 75% statistical power to detect the same differences in HBsAg seroclearance at FU Week 24.

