# 5.4.2.1. Binary Endpoints

The count and proportion (%) of participants achieving the endpoints defined in Section 5.4.1.1 will be summarized. The associated 90% CI will be included for the following endpoints:

- HBsAg seroclearance
- HBsAg seroconversion
- Suppressed HBV DNA
- ALT Normalization
- Virologic Breakthrough
- Flares

For all time points, binary endpoints will be analyzed using the observed case data. LOCF (Section 5.4.2.1.1) will be used for HBsAg seroclearance and Suppressed HBV DNA analyses at Week 24, FU Week 12, FU Week 24, FU Week 32 and FU Week 48.

The HBsAg seroclearance analyses at Week 24, FU Week 12, FU Week 24, FU Week 32 and FU Week 48 will be compared between treatment arms using a 2-sided 90% CI of the difference in proportions between the treatment groups (Arm 1 minus Arm 2) that will be constructed using a Mantel-Haenszel test controlling for stratification factor.

For single arm, point and 90% CI estimates, the Clopper Pearson method will be used.

Subsections below describe the additional analyses planned for only those specific other secondary binary endpoints that require further evaluations.

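### The 90% interval for the arm difference in seroclearance has no stated variance or zero-responder rule, and the usual Mantel-Haenszel version covers about 85% to 88% at the planned rates

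*SAP*

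**What the plan says.** The arm comparison appears in two places in the SAP.

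- **Test, SAP 5.3.2.1.1.2.** "The main estimator is constructed by using the Mantel-Haenszel test (Mantel N. et al., 1959) adjusted for the randomization stratification factor", with three screening HBsAg levels as strata, "to compare the primary endpoint between the intervention arms at a one-sided alpha level of 0.05". This is for FU Week 24.
- **Interval, SAP 5.4.2.1.** Seroclearance at Week 24 and FU Weeks 12, 24, 32 and 48 is compared through a two-sided 90% interval for Arm 1 minus Arm 2 "that will be constructed using a Mantel-Haenszel test controlling for stratification factor".

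Neither section names a variance estimator, a score or exact option, or a rule for zero responders. SAP 5.4.2 allows analyses to be skipped when data are too few, but only subgroup analyses. Single-arm intervals are Clopper-Pearson (SAP 5.1.5 and 5.4.2.1).

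The final sample is 18 in Arm 1 and 19 in Arm 2 (SAP 3). Amendment 2, written after the primary analysis, states: "Subgroup Analysis is removed due to low number of observed events of interest".

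**The concern.** A Mantel-Haenszel test does not by itself define an interval for a risk difference. A programmer would normally take the Mantel-Haenszel risk difference with a normal-theory limit and one of the two usual variances. With 37 participants, three strata and few responders, that interval is too short. With no responders it has no width.

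The difference between one and three nivolumab infusions is one of the two scientific questions in SAP 5.3.2. Under SAP 5.1.7 only 90% intervals, without tests, are given outside the FU Week 24 comparison. At the other four visits the interval is therefore the whole inferential result for this question. An interval of [0, 0] would read as exact equality of the regimens when the data say very little.

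**Working it through.** **Inputs.** n = 18 and 19 (SAP 3). Planned rates are the 1% control plus 15 and 20 points, so 16% and 21% (SAP 2 and 3). Stratum sizes are not given. Assumed per-arm splits were about 6/6/6, 3/7/8, 2/6/10, 9/6/3 and 4/8/6, plus 20 random splits of 37 and the case of a single stratum. Within each run every stratum has the same rates unless stated.

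**The plan's own figure first.** For the exact test against 1%, the critical value is 2 responders at both 0.05 and 0.025, so Hochberg does not change it. Power is 1 - (1-p)^n - n p (1-p)^(n-1). For n = 16 and p = 0.16 this is 75.1%, and for n = 20 it is 85.3%. Both stated figures reproduce. No power or precision is stated for the arm comparison.

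**Formulas.** In stratum k let x of n1 and y of n2 respond, t = x + y, N = n1 + n2, w = n1 n2/N, W = sum of w.

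- Test: sum(x - n1 t/N) / sqrt(sum V), with V = n1 n2 t (N - t) / (N²(N - 1)).
- Risk difference: d = sum w(x/n1 - y/n2) / W, with limits d ± 1.645 SE.
- Greenland-Robins variance: sum{[x(n1-x)n2³ + y(n2-y)n1³] / (n1 n2 N²)} / W².
- Sato variance: (d·sum P + sum Q) / W², with P = [n1² y - n2² x + n1 n2(n2-n1)/2] / N² and Q = [x(n2-y) + y(n1-x)] / (2N).

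**No responders.** Every t is 0, so the test numerator and sum V are both 0 and the statistic is 0/0. Also d = 0. Each Greenland-Robins term is 0, and in Sato's formula Q = 0 and P is multiplied by d = 0. Both variances are 0 and the interval is [0, 0]. For the same data the Clopper-Pearson upper limits are 1 - 0.05^(1/18) = 15.3% and 1 - 0.05^(1/19) = 14.6%. The Miettinen-Nurminen 90% interval for the difference is -12.8 to +13.4 points unstratified, and about -13 to +14 with three strata.

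**One responder, unstratified illustration.** For 1/18 against 0/19, d = 5.6 points and SE = sqrt(0.0556 × 0.9444/18) = 5.4 points, so the interval is -3.3 to +14.4. The Miettinen-Nurminen interval is about -8 to +22.

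**Exact coverage of the nominal 90% interval, three strata.** The chance of no responders is (1-p1)^18 (1-p2)^19.

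| True rates, Arm 1 / Arm 2 | No responders | Mantel-Haenszel interval | Stratified Miettinen-Nurminen |
|---|---|---|---|
| 16% / 21% | 0.05% | 84.8-85.5% (Greenland-Robins), 87.2-87.8% (Sato) | 90.0-90.2% |
| 5% / 10% | 5.4% | 80-82% (both variances) | 92.5-93.3% |
| 5% / 5% | 15% | 91-95% | about 95% |
| 3% / 3% | 32% | 95-98% | about 98% |
| 1% / 1% | 69% | over 99% | over 99% |

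In the last three rows the Mantel-Haenszel interval reaches its level partly because [0, 0] contains a true difference of 0. At 5% and 10% the zero-width outcome itself misses, and accounts for 5.4 points of the shortfall.

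At 16% and 21% overall, with responses concentrated in the low-HBsAg stratum, coverage is 83.5% to 86.2% (Greenland-Robins) or 86.7% to 88.7% (Sato). If all participants fall in one stratum, it is 88.1%, against 88.4% for Miettinen-Nurminen.

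**The case against.** **The method is unspecified rather than wrong.** Under-coverage and zero width follow from a normal-theory interval with a usual Mantel-Haenszel variance, which the SAP does not name. That stands. But the text points to no other interval, and a stratified score interval is not what a reader would infer from it.

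**The two problems belong to different scenarios.** No responders is negligible at 16% and 21%, and at equal low rates the interval does not under-cover. This stands, and the table keeps the cases apart. At 5% and 10% both occur.

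**Each arm's uncertainty is visible anyway.** The Clopper-Pearson limits near 15% would sit beside [0, 0]. They soften the misreading but do not repair the reported difference.

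**Little depends on it.** The comparison is secondary, power of the test for 21% against 16% is only about 11% to 12%, and no decision rule uses the interval. This limits the weight of the point.

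**A reader might infer that the test should be replaced by an exact one.** The calculations do not support that. With equal rates of 16% or 21% the Mantel-Haenszel test rejects in roughly 5% to 6% of trials. An exact conditional stratified test rejects in 1.5% to 2.0%, and its power for 16% against 21% falls from about 11% to 4%. The only fault shown in the test is the 0/0 case.

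**Conclusion.** The point holds for the interval in SAP 5.4.2.1. At the planned rates the usual Mantel-Haenszel interval falls about 5 points short of 90% with the Greenland-Robins variance and 2 to 3 points short with Sato. At 5% and 10% it falls 8 to 10 points short. With no responders it collapses to [0, 0] and the test in 5.3.2.1.1.2 has no p-value.

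This rests on three assumptions: stratum sizes, which did not change the conclusion over the range tried; one of the two usual variances; and denominators of 18 and 19. Section 5.4.2.1 works on observed or carried-forward data, so the real denominators could be smaller.

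Amendment 2 makes sparse data realistic. A reader might infer from it that there were no responders, or that the primary conclusion is at risk. The text says only that events of interest were few, and the primary analysis is an exact binomial test against 1% that does not use this method.

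**What to change.** - **SAP 5.4.2.1:** state that the 90% interval for the difference is the stratified Miettinen-Nurminen score interval with Mantel-Haenszel weights.
- **SAP 5.3.2.1.1.2:** keep the Mantel-Haenszel test, and add that with no responders in either arm the p-value is reported as 1 or as not estimable, choosing one.
- **SAP 6.2:** record the change. Amendment 2 followed the primary analysis, so the new interval at FU Week 24 must be labelled as chosen after those results. The same reasoning applies to the earlier visits, Week 24 and FU Week 12.

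The cost is a few sentences and a standard procedure option. Intervals become somewhat wider, and at low equal rates they are conservative (about 95% at 5% in both arms). If nearly all participants fall in one stratum, the gain at the planned rates is small (88.4% against 88.1%), but the zero-responder case is still repaired.
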